7.2.2. Exclusion Criteria

Patients meeting any of the following criteria will not be included in the study:

- e) Patients with any of the following diagnoses prior to the use of the treatments of interest or index date:
 - Valvular heart disease or valve replacement – ICD-10 codes: I05, I06, I07, I08, I09, I22, I34, I35, I36, I37, I38, I39, I700, I702-I709; Q22, Q23, Q25, T82,Z95.
 - Pregnancy during the study period. ICD-10 O00-O9A
 - Diagnosis of venous thromboembolism (VTE) – ICD-10 codes: I26, I80 - I82;
- f) Individuals with a transitory diagnosis of NVAF prior to the use of the treatments of interest or index date;
- g) Exposure to more than one OAC on or after the index date, during the follow-up period.
- h) NOAC doses different from those recommended by the manufacturing laboratories.

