I312	Haemopericardium, not elsewhere classified

B: I60, I61, I62, I85.0, I98.3, J94.2, K22.6, K25.0, K25.2, K25.4, K25.6, K26.0, K26.2, K26.4, K26.6, K27.0, K27.2, K27.4, K27.6, K28.0, K28.2, K28.4, K28.6, K29.0, K62.5, K66.1, K76.2, K92.0, K92.1, K92.2

Score 1 point

ICD-10	Description
I60	Subarachnoid haemorrhage
I61	Intracerebral haemorrhage
I62	Other nontraumatic intracranial haemorrhage
I850	Oesophageal varices with bleeding
I983	Oesophageal varices with bleeding, , not elsewhere classified
J942	Haemothorax
K226	Gastro-oesophageal laceration-haemorrhage syndrome
K250	Acute with haemorrhage
K252	Acute with both haemorrhage and perforation
K254	Chronic or unspecified with haemorrhage
K256	Chronic or unspecified with both haemorrhage and perforation
K260	Acute with haemorrhage
K262	Acute with both haemorrhage and perforation
K264	Chronic or unspecified with haemorrhage
K266	Chronic or unspecified with both haemorrhage and perforation
K270	Acute with haemorrhage
K272	Acute with both haemorrhage and perforation
K274	Chronic or unspecified with haemorrhage
K276	Chronic or unspecified with both haemorrhage and perforation
K280	Acute with haemorrhage
K282	Acute with both haemorrhage and perforation
K284	Chronic or unspecified with haemorrhage
K286	Chronic or unspecified with both haemorrhage and perforation
K290	Acute haemorrhagic gastritis
K625	Haemorrhage of anus and rectum
K661	Haemoperitoneum
K762	Central haemorrhagic necrosis of liver
K920	Haematemesis
K921	Melaena
K922	Gastro-intestinal haemorrhage, unspecified

L: INR

Score 1 point

E: Elderly \geq 65 years

Score 1 point

D: E24.4, F10, G31.2, G62.1, G72.1, I42.6, K29.2, K85.2, K86.0, T51, Y90.4, Y90.5, Y90.6, Y90.7, Y90.8, Y91.2, Y91.3, Z50.2, Z71.4, Z72.1

1 or 2 point each

ICD-10	Description
E244	Alcohol-induced pseudo-Cushing's syndrome
F10	Mental and behavioural disorders due to use of alcohol
G312	Degeneration of nervous system due to alcohol
G621	Alcoholic polyneuropathy
G721	Alcoholic myopathy
I426	Alcoholic cardiomyopathy
K292	Alcoholic gastritis
K852	Alcohol-induced acute pancreatitis
K860	Alcohol-induced chronic pancreatitis
T51	Toxic effect of alcohol
Y904	Blood alcohol level of 80-99 mg/100 ml
Y905	Blood alcohol level of 100-119 mg/100 ml
Y906	Blood alcohol level of 120-199 mg/100 ml
Y907	Blood alcohol level of 200-239 mg/100 ml
Y908	Blood alcohol level of 240 mg/100 ml or more
Y912	Severe alcohol intoxication
Y913	Very severe alcohol intoxication
Z502	Alcohol rehabilitation

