Z714	Alcohol abuse counselling and surveillance
Z721	Alcohol use

Codes Anatomical Therapeutic Chemical (ATC): B01AC, M01A

- SMAe-TT₂R₂ score:** The estimation of SAMe-TT₂R₂ will be performed by adding the following variables:

Sex (female) Score 1 point

Age (<60 years) Score 1 point

Medical history (history of more than two of the following: hypertension, diabetes, coronary artery disease or myocardial infarctions, peripheral artery disease, heart failure, stroke; pulmonary, hepatic, or renal disease) Score 1 point

Treatment (interacting medications , amiodarone ATC- C01BD01) Score 1 point

Tobacco use (within 2 years) Score 2 points

PFIZER CONFIDENTIAL

Race (non-Caucasian) Score 2 points

Table 2. Baseline variables or possible confounders

Variable	Operacional definition ICD-10
Diabetes	E10 Insulin-dependent diabetes mellitus E11 Non-insulin-dependent diabetes mellitus E12 Malnutrition-related diabetes mellitus E13 Other specified diabetes mellitus E14 Unspecified diabetes mellitus
Hypertension	I10 Essential (primary) hypertension I11 Hypertensive heart disease I12 Hypertensive renal disease I13 Hypertensive heart and renal disease I15 Secondary hypertension
Ischaemic stroke	I63 Cerebral infarction Excepto I636 Cerebral infarction due to cerebral venous thrombosis, nonpyogenic I64 Stroke, not specified as haemorrhage or infarctionz
Haemorrhagic stroke	I60 Subarachnoid haemorrhage I61 Intracerebral haemorrhage I62 Other nontraumatic intracranial haemorrhage

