Bleeding (gastrointestinal, intracranial, other)	I60 Subarachnoid haemorrhage I61 Intracerebral haemorrhage I62 Other nontraumatic intracranial haemorrhage S064 Epidural haemorrhage S065 Traumatic subdural haemorrhage S066 Traumatic subarachnoid haemorrhage I850 Oesophageal varices with bleeding K250 Acute with haemorrhage K252 Acute with both haemorrhage and perforation K254 Chronic or unspecified with haemorrhage K256 Chronic or unspecified with both haemorrhage and perforation K260 Acute with haemorrhage K262 Acute with both haemorrhage and perforation K264 Chronic or unspecified with haemorrhage K266 Chronic or unspecified with both haemorrhage and perforation K270 Acute with haemorrhage K272 Acute with both haemorrhage and perforation K274 Chronic or unspecified with haemorrhage K276 Chronic or unspecified with both haemorrhage and perforation K280 Acute with haemorrhage K282 Acute with both haemorrhage and perforation K284 Chronic or unspecified with haemorrhage K286 Chronic or unspecified with both haemorrhage and perforation K290 Acute haemorrhagic gastritis K625 Haemorrhage of anus and rectum K920 Haematemesis K921 Melaena K922 Gastro-intestinal haemorrhage, unspecified D62 Acute posthaemorrhagic anaemia H356 Retinal haemorrhage H431 Vitreous haemorrhage H450 Vitreous haemorrhage in diseases classified elsewhere H922 Otorrhagia

PFIZER CONFIDENTIAL

Variable	Operacional definition ICD-10
	I312 Haemopericardium, not elsewhere classified J942 Haemothorax R04 Haemorrhage from respiratory passages K661 Haemoperitoneum M250 Haemarthrosis N02 Recurrent and persistent haematuria N938 Other specified abnormal uterine and vaginal bleeding N939 Abnormal uterine and vaginal bleeding, unspecified N950 Postmenopausal bleeding R31 Unspecified haematuria R58 Haemorrhage, not elsewhere classified T792 Traumatic secondary and recurrent haemorrhage
Systemic embolism	I74 Arterial embolism and thrombosis
Alcohol consumption	E244 Alcohol-induced pseudo-Cushing's syndrome E52 Niacin deficiency [pellagra] G312 Degeneration of nervous system due to alcohol G621 Alcoholic polyneuropathy G721 Alcoholic myopathy I426 Alcoholic cardiomyopathy K292 Alcoholic gastritis K70 Alcoholic liver disease K860 Alcohol-induced chronic pancreatitis O354 Maternal care for (suspected) damage to foetus from alcohol T51 Toxic effect of alcohol Z714 Alcohol abuse counselling and surveillance Z721 Alcohol use

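### The Table 2 alcohol consumption list and the alcohol codes in HAS-BLED item D differ in both directions; Table 2 lacks F10 and nine other codes that the protocol itself counts as alcohol use

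*Combined protocol and SAP*

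**What the plan says.** Alcohol appears in three places in the protocol.

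- **HAS-BLED score, item D (Section 7.3.1).** The alcohol codes are "D: E24.4, F10, G31.2, G62.1, G72.1, I42.6, K29.2, K85.2, K86.0, T51, Y90.4, Y90.5, Y90.6, Y90.7, Y90.8, Y91.2, Y91.3, Z50.2, Z71.4, Z72.1". The description table beneath lists the same 20 codes. Item D also scores drugs, through the line "Codes Anatomical Therapeutic Chemical (ATC): B01AC, M01A".
- **Table 2 (baseline variables or possible confounders), alcohol consumption.** This list of 13 codes begins "E244 Alcohol-induced pseudo-Cushing's syndrome E52 Niacin deficiency [pellagra] G312 Degeneration of nervous system due to alcohol". It also contains "K292 Alcoholic gastritis K70 Alcoholic liver disease" and "O354 Maternal care for (suspected) damage to foetus from alcohol". F10 is not in it.
- **Table 1 (Section 7.3).** A Yes/No field records high alcohol intake at the date of OAC prescription. Its source is the medical record and it has no ICD-10 list.

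The exclusion criteria (Section 7.2.2) remove "Patients with any of the following diagnoses prior to the use of the treatments of interest or index date", and one entry in that group is "Pregnancy during the study period. ICD-10 O00-O9A".

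The protocol does not say how the three alcohol measures relate to one another.

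**The concern.** Describing clinical characteristics is a primary objective, and alcohol is both a baseline variable in Table 2 and a component of a baseline bleeding-risk score. If one protocol applies two code lists to one concept, the same record can be alcohol-positive under one and negative under the other. The gap includes F10, the code for mental and behavioural disorders due to alcohol, as well as alcohol rehabilitation (Z50.2), alcohol-induced acute pancreatitis (K85.2) and all the blood-alcohol and intoxication codes. The presence of a code from an excluded block suggests that the Table 2 list was not checked against the eligibility criteria. What is at stake is the classification of one baseline covariate and whether it can be read alongside HAS-BLED.

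**Working it through.** **Inputs.** The two code lists in Section 7.3.1 and Table 2, and the exclusion block O00-O9A in Section 7.2.2. The plan states no figure on this point, so there is none to reproduce.

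**Set comparison.**

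| Set | Codes | Count |
|---|---|---|
| Item D | full list | 20 |
| Table 2 | full list | 13 |
| In both | E24.4, G31.2, G62.1, G72.1, I42.6, K29.2, K86.0, T51, Z71.4, Z72.1 | 10 |
| Item D only | F10, K85.2, Y90.4, Y90.5, Y90.6, Y90.7, Y90.8, Y91.2, Y91.3, Z50.2 | 20 − 10 = 10 |
| Table 2 only | E52, K70, O35.4 | 13 − 10 = 3 |
| Either list | | 20 + 13 − 10 = 23 |

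Table 2 holds 13 of the 23 codes and item D holds 20 of the 23.

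**The three codes found only in Table 2.**

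- O35.4 lies inside O00-O9A. Under the exclusion lead-in, a patient with that code before the index date is not eligible, so the code identifies nobody at baseline.
- K70 (alcoholic liver disease) is absent from item D but is listed in HAS-BLED under the liver item A, so it already scores one point there.
- E52 is described only as niacin deficiency (pellagra), with no mention of alcohol.

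**Direction and size.** The documents give no prevalence for any of these codes, so the following are assumptions for illustration only. Take N = 7,500 (Section 7.5). Let s = 0.5% be the share of patients with a shared code, a the share identified only by the ten item-D-only codes, and b the share identified only by K70 or E52. Then:

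- Table 2 positive = N(s + b)
- Item D alcohol positive = N(s + a)
- Positive on either list = N(s + a + b)
- Classified differently = N(a + b)

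| a | b | Table 2 | Item D | Either | Classified differently |
|---|---|---|---|---|---|
| 1% | 0 | 37.5 | 112.5 | 112.5 | 75 |
| 1% | 1% | 112.5 | 112.5 | 187.5 | 150 |
| 0.25% | 1% | 112.5 | 56.25 | 131.25 | 93.75 |

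Table 2 falls below item D only when a > b. It falls below the combined list whenever a > 0. With a from 0.25% to 3% and b from 0 to 3%, Table 2 captures between 37.5/262.5 = 14% and 262.5/281.25 = 93% of the combined list.

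**The case against.** The strongest reply is that the two lists serve different variables. Item D is a drugs-or-alcohol component of a score, and no alcohol-only figure from HAS-BLED is planned, so no pair of published numbers would visibly disagree. Table 1 takes high alcohol intake from the chart, and Section 7.4.2 makes the medical record the source of baseline clinical characteristics. A patient coded F10 is therefore not necessarily reported as having no alcohol problem. Section 7.7 rules out treatment comparison, so no adjusted estimate depends on the Table 2 list. The absence of K70 from item D is not evidently an error, because the code already scores under liver item A.

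All of that stands, and it limits the point to one descriptive covariate. It does not explain why a variable called alcohol consumption omits codes that the same protocol reads as alcohol use. The chart field does not close the gap either: high intake at a given date and a coded alcohol-related diagnosis are different things, and no rule links them.

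A reader might go further and infer that Table 2 understates alcohol use relative to HAS-BLED, perhaps by half or more. The documents do not support this. The lists differ in both directions, the net difference depends on unstated prevalences, and the illustration gives results either way. O35.4 cannot contribute to any shortfall, since it is inert. A reader might also conclude that a single identical list should be used in both places. Putting K70 into item D would let one code score under both A and D.

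**Conclusion.** The point holds as an unreconciled definition. Ten codes, including F10, count as alcohol use in HAS-BLED item D but not in Table 2. Three codes stand only in Table 2: one is inert and one has a description that does not mention alcohol. Patients identified solely by any of the ten omitted codes are negative for Table 2 alcohol consumption, so that variable falls short of the protocol's own combined alcohol codes if there is even one such patient.

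The code counts are certain. The number of patients affected is unknown, and the 14% to 93% range rests wholly on assumed prevalences. To call the two variables contradictory would be too strong; the accurate statement is that they can classify the same patient differently on alcohol. This is a modest point that is worth correcting because the correction is nearly free.

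**What to change.** In Table 2, alcohol consumption:

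1. Add F10, K85.2, Y90.4 to Y90.8, Y91.2, Y91.3 and Z50.2.
2. Delete O35.4.
3. Keep K70 here, and do not add it to HAS-BLED item D, because it already scores under liver item A.
4. Confirm E52 with a stated reason, or drop it.

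The list then has 13 + 10 − 1 = 22 codes, or 21 without E52. HAS-BLED item D stays as it is.

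Add one sentence saying that the Table 1 chart field on high alcohol intake is reported as a separate variable from the code-based one, and that neither overrides the other.

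The cost is a code-list edit and that one sentence, with no change to data sources, study size or the score. It is best done before the variables are derived.

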Leukemia	Clinical characteristic	Medical record	Yes, No

PFIZER CONFIDENTIAL

Variable	Role	Data source (s)	Operational definition
Malignant lymphoma	Clinical characteristic	Medical record	Yes, No
Peptic ulcer disease	Clinical characteristic	Medical record	Yes, No
Metastatic solid tumor	Clinical characteristic	Medical record	Yes, No
History of ischemic or hemorrhagic stroke	Clinical characteristic	Medical record	Yes, No
History of TIA	Clinical characteristic	Medical record	Yes, No
History of de tromboembolismo	Clinical characteristic	Medical record	Yes, No
Enfermedad coronaria	Clinical characteristic	Medical record	Yes, No
History of de hemorragia gastrointestinal	Clinical characteristic	Medical record	Yes, No
History of Intracranial bleeding	Clinical characteristic	Medical record	Yes, No
History of Other bleeding	Clinical characteristic	Medical record	Yes, No
Bleeding history or predisposition at start OAC treatment	Clinical characteristic	Medical record	Yes, No
INR > 60% at start OAC treatment	Clinical characteristic	Medical record	Yes, No
Use of aspirin at start OAC treatment	Clinical characteristic	Medical record	Yes, No
Use of clopidogrel at start OAC treatment	Clinical characteristic	Medical record	Yes, No
Use of NSAIDs at start OAC treatment	Clinical characteristic	Medical record	Yes, No
HASBLED at start OAC treatment	Clinical characteristic	Medical record	Score – number higher than 0
CHA2DS2-VASc at start OAC treatment	Clinical characteristic	Medical record	Score – number higher than 0
Anaemia at start OAC treatment	Clinical characteristic	Medical record	Yes, No
Stroke	Clinical outcome	Medical record	Yes, No
Time to stroke	Clinical outcome	Medical record	Date of event dd/mm/yy

Pfizer Confidential

Variable	Role	Data source (s)	Operational definition
Type of stroke	Clinical outcome	Medical record	Ischemic stroke, Haemorrhagic or not specified
Pulmonary embolism	Clinical outcome	Medical record	Yes, No
Time to pulmonary embolism	Clinical outcome	Medical record	Date of event dd/mm/yy
Gastrointestinal bleeding	Clinical outcome	Medical record	Yes, No
Time to gastrointestinal bleeding	Clinical outcome	Medical record	Date of event dd/mm/yy
Intracranial bleeding	Clinical outcome	Medical record	Yes, No
Time to Intracranial bleeding	Clinical outcome	Medical record	Date of event dd/mm/yy
Other major bleeding	Clinical outcome	Medical record	Yes, No
Time to other major bleeding	Clinical outcome	Medical record	Date of event dd/mm/yy
CCI			

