K272	Acute with both haemorrhage and perforation
K274	Chronic or unspecified with haemorrhage
K276	Chronic or unspecified with both haemorrhage and perforation
K280	Acute with haemorrhage
K282	Acute with both haemorrhage and perforation
K284	Chronic or unspecified with haemorrhage
K286	Chronic or unspecified with both haemorrhage and perforation
K290	Acute haemorrhagic gastritis
K625	Haemorrhage of anus and rectum
K920	Haematemesis
K921	Melaena
K922	Gastro-intestinal haemorrhage, unspecified
D62	Acute posthaemorrhagic anaemia
H356	Retinal haemorrhage
H431	Vitreous haemorrhage
H450	Vitreous haemorrhage in diseases classified elsewhere
H922	Otorrhagia
I312	Haemopericardium, not elsewhere classified
J942	Haemothorax
R04	Haemorrhage from respiratory passages
K661	Haemoperitoneum
M250	Haemarthrosis
N02	Recurrent and persistent haematuria
N938	Other specified abnormal uterine and vaginal bleeding
N939	Abnormal uterine and vaginal bleeding, unspecified
N950	Postmenopausal bleeding
R31	Unspecified haematuria
R58	Haemorrhage, not elsewhere classified
T792	Traumatic secondary and recurrent haemorrhage

- Ischemic stroke:** Patients who report the following diagnoses in the medical history during the follow-up period:

ICD-10	Description
I63	Cerebral infarction
I64	Stroke, not specified as haemorrhage or infarction

Except I63.6 Cerebral infarction due to thrombosis of cerebral veins, non-pyogenic

- Hemorrhagic stroke:** Patients presenting the following diagnosis in the medical record:

PFIZER CONFIDENTIAL

ICD-10	Description
I60	Subarachnoid haemorrhage
I61	Intracerebral haemorrhage
I62	Other nontraumatic intracranial haemorrhage

- **Systemic embolism:** Patients who report any of the following diagnoses:

ICD-10	Description
I74	Arterial embolism and thrombosis

Definition of covariates

- **Age:** Categorical variable, continues in years. It will be defined from the index date and will be used to assign patients to the following age categories:

18 - 49
 50 - 59
 60 - 69
 70 - 79
 ≥ 80 years old.

- **Charlson Index:** Charlson comorbidity index will be created during the reference period taking into account the following score:

1 point each:

- *Myocardial infarction*

ICD-10	Description
I21	Acute myocardial infarction
I22	Subsequent myocardial infarction
I252	Old myocardial infarction

- *Congestive heart failure*

ICD-10	Description
I110	Hypertensive heart disease with (congestive) heart failure

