ICD-10	Description
N032	Diffuse membranous glomerulonephritis
N033	Diffuse mesangial proliferative glomerulonephritis
N034	Diffuse endocapillary proliferative glomerulonephritis
N035	Diffuse mesangiocapillary glomerulonephritis
N036	Dense deposit disease
N037	Diffuse crescentic glomerulonephritis
N052	Diffuse membranous glomerulonephritis
N053	Diffuse mesangial proliferative glomerulonephritis
N054	Diffuse endocapillary proliferative glomerulonephritis
N055	Diffuse mesangiocapillary glomerulonephritis
N056	Dense deposit disease
N057	Diffuse crescentic glomerulonephritis
N18	Chronic renal failure
N19	Unspecified renal failure
N250	Renal osteodystrophy
Z490	Preparatory care for dialysis
Z492	Other dialysis
Z940	Kidney transplant status
Z992	Dependence on renal dialysis

A: B18, I85, I86.4, I98.2, K70, K71.1, K71.3, K71.4, K71.5, K71.7, K72.1, K72.9, K73, K74, K76.0, K76.2, K76.3, K76.4, K76.5, K76.6, K76.7, K76.8, K76.9, Z94.4

Score 1 point

ICD-10	Description
B18	Chronic viral hepatitis
I85	Oesophageal varices
I864	Gastric varices
I982	Oesophageal varices in diseases classified elsewhere
K70	Alcoholic liver disease
K711	Toxic liver disease with hepatic necrosis
K713	Toxic liver disease with chronic persistent hepatitis
K714	Toxic liver disease with chronic lobular hepatitis
K715	Toxic liver disease with chronic active hepatitis
K717	Toxic liver disease with fibrosis and cirrhosis of liver
K721	Chronic hepatic failure
K729	Hepatic failure, unspecified
K73	Chronic hepatitis, not elsewhere classified
K74	Fibrosis and cirrhosis of liver
K760	Fatty (change of) liver, not elsewhere classified
K762	Central haemorrhagic necrosis of liver
K763	Infarction of liver
K764	Peliosis hepatis
K765	Hepatic veno-occlusive disease
K766	Portal hypertension
Z944	Liver transplant status

S: I64, I69.3, D62, D68.3, D69.8, D69.9, H31.3, H35.6, H43.1, H45.0, H92.2, I23.0, I31.2

Score 1 point

PFIZER CONFIDENTIAL

ICD-10	Description
I64	Stroke, not specified as haemorrhage or infarction
I693	Sequelae of cerebral infarction
D62	Acute posthaemorrhagic anaemia
D683	Haemorrhagic disorder due to circulating anticoagulants
D698	Other specified haemorrhagic conditions
D699	Haemorrhagic condition, unspecified
H313	Choroidal haemorrhage and rupture
H356	Retinal haemorrhage
H431	Vitreous haemorrhage
H450	Vitreous haemorrhage in diseases classified elsewhere
H922	Otorrhagia
I230	Haemopericardium as current complication following acute myocardial infarction

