Peripheral artery disease	I702 Atherosclerosis of arteries of the extremities I708 Atherosclerosis of other arteries I709 Generalised and unspecified atherosclerosis
Anaemia	D50 Iron deficiency anaemia D51 Vitamin B12 deficiency anaemia D52 Folate deficiency anaemia D53 Other nutritional anaemias D55 Anaemia due to enzyme disorders D56 Thalassaemia D57 Sickle-cell disorders D58 Other hereditary haemolytic anaemias D59 Acquired haemolytic anaemia
Congestive heart failure	I110 Hypertensive heart disease with (congestive) heart failure I130 Hypertensive heart and renal disease with (congestive) heart failure I132 Hypertensive heart and renal disease with both (congestive) heart failure and renal failure
Renal disease	B15 Acute hepatitis A B16 Acute hepatitis B B17 Other acute viral hepatitis B18 Chronic viral hepatitis B19 Unspecified viral hepatitis C22 Malignant neoplasm of liver and intrahepatic bile ducts K70 Alcoholic liver disease K71 Toxic liver disease K72 Hepatic failure, not elsewhere classified K73 Chronic hepatitis, not elsewhere classified K74 Fibrosis and cirrhosis of liver

PFIZER CONFIDENTIAL

Variable	Operacional definition ICD-10
	K75 Other inflammatory liver diseases K76 Other diseases of liver K77 Liver disorders in diseases classified elsewhere Z944 Liver transplant status
Myocardial infarction	I21 Acute myocardial infarction I22 Subsequent myocardial infarction I252 Old myocardial infarction
Peripheral vascular disease	I70 Atherosclerosis I71 Aortic aneurysm and dissection I731 Thromboangiitis obliterans [Buerger] I738 Other specified peripheral vascular diseases I739 Peripheral vascular disease, unspecified I771 Stricture of artery I790 Aneurysm of aorta in diseases classified elsewhere I792 Peripheral angiopathy in diseases classified elsewhere K551 Chronic vascular disorders of intestine K558 Other vascular disorders of intestine K559 Vascular disorder of intestine, unspecified Z958 Presence of other cardiac and vascular implants and grafts Z959 Presence of cardiac and vascular implant and graft, unspecified
TIA	G450 Vertebro-basilar artery syndrome G458 Other transient cerebral ischaemic attacks and related syndromes G451 Carotid artery syndrome (hemispheric) G459 Transient cerebral ischaemic attack, unspecified
Coronary artery disease	I20 Angina pectoris I21 Acute myocardial infarction

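### The Table 2 Anaemia row omits D62, so a patient whose only anaemia code is D62 counts as bleeding but not as anaemic

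*Combined protocol and SAP*

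**What the plan says.** Table 1 (Section 7.3) lists "Anaemia at start OAC treatment" as a clinical characteristic taken from the medical record and coded yes or no. It gives no code list and no laboratory threshold.

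Table 2, at the end of Section 7.3.1, gives ICD-10 definitions for baseline variables and possible confounders. Its Anaemia row opens with four deficiency and nutritional codes, goes on to three codes for enzyme and haemoglobin disorders (D55 to D57), and closes with "D58 Other hereditary haemolytic anaemias D59 Acquired haemolytic anaemia". The next row, congestive heart failure, follows directly.

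D62 appears in three other lists in Section 7.3.1:

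- the Bleeding row of the same Table 2: "D62 Acute posthaemorrhagic anaemia H356 Retinal haemorrhage"
- the major bleeding outcome list, where D62 is described as "Acute posthaemorrhagic anaemia"
- the HAS-BLED code list, which reads in part "S: I64, I69.3, D62, D68.3, D69.8, D69.9"

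**The concern.** By its own label, D62 is an anaemia caused by bleeding. The protocol extracts it at baseline but does not count it in the row that defines anaemia. In a study of anticoagulated patients this is an odd code to leave out, all the more because the row does include hereditary forms such as D56 and D57.

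Describing clinical characteristics at the start of treatment is a primary objective (Section 6), and anaemia is one of the characteristics listed. If the Table 2 codes are applied as written, the reported percentage with anaemia is too low, and the baseline table can show the same patient as having bled but not being anaemic on the strength of a single code that names both.

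**Working it through.** There is no planned figure to reproduce. The check compares the code lists and then sizes the gap.

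**1. Codes in the Anaemia row.** D50, D51, D52, D53, D55, D56, D57, D58 and D59, which is nine codes. D62 is absent. The heart failure row comes straight after D59, with no sign of lost or redacted text.

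**2. Where D62 is used.** It is in the Table 2 Bleeding row (baseline), the major bleeding list (follow-up) and HAS-BLED component S. That is three lists, none of which defines anaemia.

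**3. Could D62 be absent because it was assigned to Bleeding instead?** Only if each code belonged to one row. Table 2 does not work that way. I60 to I62 stand under both haemorrhagic stroke and Bleeding, and I21 stands under both myocardial infarction and coronary artery disease. No rule of exclusivity is stated.

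**4. Who is affected under the code definition.**

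- D62 plus any of the nine codes: anaemia yes, bleeding yes. Classified correctly.
- Blood-loss anaemia recorded as iron deficiency: captured by D50, which is listed without excluding any subcode.
- D62 and none of the nine codes: anaemia no, bleeding yes. This is the only group affected.

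**5. Size.** Let s be the share of patients in that last group.

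- Reported anaemia percentage = percentage under the ten-code list (the nine plus D62) − s
- Patients missed = s × 7,500, with 7,500 from Section 7.5

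The documents do not give s, so the values below are assumptions that only show the scale:

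| s (assumed) | s × 7,500 | patients missed |
|---|---|---|
| 0.5% | 0.005 × 7,500 = 37.5 | about 38 |
| 1% | 0.01 × 7,500 | 75 |
| 3% | 0.03 × 7,500 | 225 |

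**6. Where the variable goes next.** The Anaemia row feeds no eligibility criterion and no outcome. It also feeds none of the four scores (Charlson, CHA2DS2-VASc, HAS-BLED, SAMe-TT2R2); HAS-BLED reads D62 directly. Section 7.7 rules out a treatment comparison and specifies no adjusted model that uses anaemia.

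**The case against.** The strongest reply is that the omission may change nothing in the data. Table 1 takes anaemia as yes or no from the medical record, Section 7.4.2 assigns baseline clinical characteristics to that source, and Section 7.6.1 has trained physicians abstract the charts. A physician who reads a note of anaemia after haemorrhage could well enter yes, whatever Table 2 lists. This stands in part: misclassification is not certain. It does not remove the point. Table 2 holds the only written operational definition of anaemia, Section 7.6.1 says the variables are to be set according to the protocol, and nothing says that chart judgement overrides the codes.

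A second reply is that D62 patients are not lost, since they appear under Bleeding and D62 also enters HAS-BLED. That is correct and limits the harm: the bleeding history is kept, and only the anaemia count is affected.

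A reader might also infer two stronger things that the documents do not support. One is that patients with blood-loss anaemia in general are recorded as not anaemic. The nine codes include D50, so only patients with D62 and no listed code are at issue. The other is that the row misses a larger group because it stops before the remaining codes after D59. D62 is the only later anaemia code that the documents describe. What the others contain, and how often they are used, cannot be established from the documents, so no count can be put on them here. It is still reasonable to ask the sponsor whether the row was meant to end at D59.

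**Conclusion.** The point holds in a limited form. The Table 2 Anaemia row is inconsistent with the protocol's own label for D62, and the overlap between other rows means that placing D62 under Bleeding does not explain the gap. If the Table 2 codes decide, baseline anaemia is understated by exactly the share of patients with D62 and none of the nine listed codes. The counts of about 38 to 225 rest wholly on the assumed range of 0.5% to 3%. If the chart field decides, the understatement may be smaller or nil, and the documents leave that open.

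The consequence is one descriptive percentage under a primary objective, and one possible confounder. No score, outcome, eligibility decision or planned treatment comparison depends on it. It is worth correcting because the inconsistency is plain and the correction is nearly free.

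**What to change.** 1. Add D62 to the Anaemia row of Table 2, which makes ten codes. If it is left out on purpose, say that it is counted only as bleeding and why.
2. Confirm whether the row was meant to stop at D59.
3. State in Section 7.3 whether the Table 2 codes or the Table 1 chart field decides anaemia at the start of treatment, and what is done when they disagree. Any clear rule will do, provided it is fixed before abstraction begins.

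The cost is one code in one row and a sentence or two of text. No new data source is needed, because D62 is already sought for the Bleeding row. The abstraction form and its instructions should carry the same definition.
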